Investigational Tobacco Product

The Co-PIs of this project, Drs. [name] and [name], will apply for an Investigational Tobacco Product (ITP) application to the FDA to cover the experimental cigarettes being used in this study.

Certificate of Confidentiality

To help protect the participant's privacy, Drs. [name] and [name] have obtained for a Certificate of Confidentiality from the National Institutes of Health. With this certificate, the researchers cannot be forced to disclose information that may identify the participants, even by a court subpoena, in any federal, state, or local civil, criminal, administrative, legislative, or other proceedings. The researchers will use the Certificate to resist any demands for information that would identify the participants, except as explained below. The Certificate cannot be used to resist a demand for information from personnel of the United States Government that is used for auditing or evaluation of federally funded projects or for information that must be disclosed in order to meet the requirements of the Federal Food and Drug Administration (FDA).

The Certificate of Confidentiality does not prevent the participant or a member of their family from voluntarily releasing information about themselves and their involvement in the research. If an insurer, employer or other person obtains the participant's written consent to receive research information, then the researcher may not use the Certificate to withhold that information. The Certificate of Confidentiality does not prevent the researchers from disclosing voluntarily, without consent, information that would identify the individual as a participant of the research project in instances such as evidence of child abuse or a participant's threatened violence to self or others.

Outcome Variables

Primary Outcome Variables:

- Number of cigarette puffs

Secondary Outcome Variables:

- Number of vaping device puffs
- CO boost

Exploratory Outcome Variables:

- Number of choices for cigarette puffs
- Number of choices for e-cig puffs
- Number of choices to abstain from puffing
- Measures of compliance: drop-out rate
- Measures of discomfort/dysfunction: MNWS, QSU, PANAS
- Measures of cigarette characteristics: CES, Cigarette Purchase Task
- Measures of perceived risk: Perceived Health Risk Scale
- Measures of cardiovascular function: heart rate, blood pressure
- Biomarkers: TNE, NMR, Cotinine, CO

Statistical Approach

Demographics and baseline data will be compared between the groups randomized to NNC or VLNC cigarettes using t-tests and chi-square tests. The endpoints of interest are the number of puffs from cigarettes, the number of puffs from e-cigs, and the number of choices to abstain from both cigarettes and e-cigs. Descriptive statistics will summarize the data by cigarette group and by session. Results will be presented in tabular and graphical format.

The **primary aim** is to examine the effects of cigarette nicotine content, e-cig nicotine concentration and e-cig flavor on choices to smoke. The primary outcome measure is the number of cigarette puffs, and the secondary outcomes are the number of e-cig puffs, and CO boost.

The **secondary aim** is to examine the effects of these factors on product appeal and sensory effects (Cigarette/E-Cig Evaluation Scale), perceived health risks (Perceived Health Risks Assessment), and pre- to post-use changes in craving (QSU), withdrawal symptoms (MNWS), and affect (PANAS). The primary statistical model to test both aims will be a linear mixed model carried out according to the $2 \times 2 \times 2$ design, where the between-subject factor is NNC or VLNC cigarettes and the two within-subject factors relate to e-cig flavor (cigarette or non-cigarette) and nicotine concentration (very low or moderate). The session where no e-cigs are included will be analyzed separately by comparing choices for NNC vs. VLNC cigarettes using a two sample t-test with unequal variances. The mixed model for the balanced factorial design will allow for the evaluation of the three main effects and their interactions. The major concern for this

approach is the occurrence of non-constant variance for the number of puffs of each product or the number of times abstaining as the dependent variables. Therefore, sensitivity analyses will be performed to evaluate the robustness of our assumptions. A generalized estimating equation (GEE) model uses sandwich estimators and thus is less affected by unequal variances, however, it is more negatively impacted by the occurrence of missing observations. Additionally, a negative binomial regression approach will check if modeling the number of puffs as a count variable provides a better fit to the data. The first mixed model will assume that participant characteristics are balanced between groups due to randomization and include only the three main effects and their interactions.

Subsequent analyses will add in participant factors including gender, baseline CPD, and nicotine dependence as potential moderators of study outcomes (**Exploratory Aim**). Possible interactions between the main effects and these covariates will be investigated. To test whether the use of e-cigs mediates the decrease in cigarette smoking and CO exposure, a causal model such as the marginal structural model (MSM) will be considered.

The primary analysis of all endpoints will adhere to the intent-to-treat principle where all participants will be included in the analysis according to the group to which they were randomly assigned. A secondary per-protocol analysis will include only participants who complete all 5 sessions.

Power Analysis

Very little has been reported in the literature on the effect of VLNC cigarettes or the dual use of e-cigs on adolescent smokers that could guide sample sizes for the proposed study. To determine a reasonable effect size (ES=mean difference/common SD) for sample size calculations, we considered several recent studies investigating alternatives to usual brand cigarettes in adolescents and young adults. In the first phase on CENIC (Project 1), CPD at weeks 2 and 6 were recorded for adult smokers using cigarettes with the same level of nicotine planned for our current project (15.8 mg/g vs 0.4 mg/g). Selecting out the youngest participants (18-24 years of age), the comparison between these two nicotine groups resulted in an ES of 0.76 at 2 weeks and 0.85 at 6 weeks. A recent study of adolescent smokers (Cassidy et al., 2015) used a very similar design as the current proposal. Participants made a series of 20 choices between puffs of their usual brand cigarettes or money, where the amount of money varied over three sessions (\$0.00, \$0.10, \$0.50). The ES for the comparison between 10 and 50 cents was .73. Therefore, we determined that n=60 in each cigarette group would allow for the detection of an ES of 0.60 or higher with statistical power of at least 90% for a two-sided, two-sample test where the significance level is 0.05. For the within-subject comparisons defined by the 2 e-cig factors, an ES of 0.5 or more for the two main effects would have at least 97% power in a repeated measures analysis if n=60 per cigarette group with a significance level of 0.05. Study enrollment will continue until 60 subjects completing all 6 sessions in each group. Sample size and power calculations were carried out using PASS 13 (NCSS, LLC. Kaysville, Utah, 2014).

Subject Identifier

The subject identifier is an alpha-numeric combination. Example: G-C001 would be Brown University's first subject.

Project Identifier:

H = Project 3

Site Identifier:

C = Brown University

Subject ID:

001-899

Data Collection Time Points Identification Numbers:

92= Screening/Baseline Session

01= Lab Session 1

02= Lab Session 2

03= Lab Session 3

04= Lab Session 4

05= Lab Session 5

30= 30 day follow-up phone call

99= Unscheduled visit

Data Storage

Data will be stored locally at Brown University and at the University of Minnesota Masonic Cancer Center's Bioinformatics Core for at least 7 years after study completion.

References

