Lab Sessions 2-5 will each include a preference task in which two products are available. In the sampling phase, participants will sample and then rate the same combusted cigarette type from Lab Session 1 and will also sample and rate an e-cig with the assigned combination of characteristics for that session (i.e., 3 mg/mL nicotine + cigarette flavor; 3 mg/mL nicotine + non-cigarette flavor; 18 mg/mL nicotine + cigarette flavor; or 18 mg/mL nicotine + non-cigarette flavor). E-liquid nicotine concentration will be administered under double-blind conditions; flavors, by necessity, will not be blinded. In the preference phase, participants will be prompted via computerized instructions to make a series of 10 choices. Each choice will be to either take 2 cigarette puffs, 2 e-cig puffs, or to abstain from puffing; again, a total of 20 puffs (from either or both products) is available (tasks are described in greater detail below). Between lab sessions, participants will be instructed to return to their usual tobacco use patterns.

Design Schematic					
NNC cigarettes (n=60): 5 sessions			VLNC cigarettes (n=60): 5 sessions		
e-liquid nic concentration	e-liquid flavors	e-liquid flavors	e-liquid nic concentration	e-liquid flavors	e-liquid flavors
3 mg/ml	x	x	3 mg/ml	x	x
18 mg/ml	x	x	18 mg/ml	x	x
No e-cig	x		No e-cig	x	

Summary of Measures

MEASURES	SCREEN/ BL	LAB SESSIONS				
		1	2	3	4	5
QUESTIONNAIRES AND MONITORING						
Demographics Questionnaire	X					
Medical History Questionnaire & Follow-Up Questionnaire	X					
MINI Suicide Subscale	X					
Tobacco Use History Questionnaire	X					
Vaping History Questionnaire	X					
Timeline Follow Back (TLFB): Baseline and Lab Session Versions	X	X	X	X	X	X
Contemplation Ladder	X					
Drug Use History Questionnaire	X					
Depressive Symptoms (CES-D)	X					
Fagerstrom Test for Nicotine Dependence (FTND)	X					
Cigarette Dependence Questionnaire	X					
Environmental Tobacco Smoke (ETS) Questionnaire	X					
Smoking/Vaping Identity	X					
Smoking Expectancies Questionnaire	X					
Respiratory Health (ATSQ)	X					
Predicted Behavior Interview						X
Adverse Events		X	X	X	X	X
End of Study Questionnaire						X
LABORATORY PREFERENCE TASK						
Questionnaire on Smoking Urges (QSU)- Brief	X	X	X	X	X	X
Minnesota Nicotine Withdrawal Scale (MNWS)	X	X	X	X	X	X
Positive and Negative Affect Scale (PANAS)	X	X	X	X	X	X
Cigarette Evaluation Scale (CES)	X	X	X	X	X	X
Vaping Expectancies Questionnaire (VEQ)	X					

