5.1. Primary Endpoint

- Number of cigarette puffs taken: Among the 5 sessions, the first session is always cigarettes only, no e-cigs, and each of the 10 choices is between taking 2 cigarette puffs or abstaining from smoking. At each session where e-cigs are available (i.e., Sessions 2-5), each of the 10 choices is between taking 2 cigarette puffs, 2 e-cig puffs, or abstaining from both. The maximum number of cigarette puffs taken will be 20 for each of the five sessions.

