5.3. Exploratory Endpoints

- Number of choices for cigarette puffs (0 to 10)
- Number of choices for e-cig puffs (0 to 10)
- Number of choices to abstain from puffing (0 to 10)
- Measures of compliance: drop-out rate
- Measures of discomfort/dysfunction: MNWS, QSU, PANAS
- Measures of cigarette characteristics: CES, Cigarette Purchase Task indices
- Measures of perceived risk: Perceived Health Risk Scale
- Measures of cardiovascular function: heart rate, blood pressure
- Biomarkers: TNE, NMR, Cotinine, CO

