6.3. Primary Endpoint Analysis

The primary endpoint is the total number of puffs of their study cigarette taken at each of the 5 laboratory sessions. The participant can have up to 20 puffs on the cigarette and, therefore, the result is an integer that ranges from 0 to 20.

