6.3.1. Primary Analysis

Descriptive statistics will summarize the number of cigarette puffs by cigarette group and by session. Results will be presented in tabular and graphical format. The primary statistical model will be a linear mixed model (2) carried out according to the 2 x 2 x 2 design, where the between-subject factor is NNC or VLNC cigarettes and the two within-subject factors relate to e-cig flavor (cigarette or non-cigarette flavors) and nicotine content (very low or moderate). The session where no e-cigs are included will be analyzed separately by comparing the normal and reduced nicotine cigarettes groups using linear regression adjusting for baseline CPD from TLFB to improve precision. Sandwich standard

errors will be used to account for potential heteroscedasticity. Data from the four sessions where e-cigs are available will be analyzed using a linear mixed model to account for potential correlation between repeated measures on an individual. The mixed model for the balanced factorial design will allow for the evaluation of the three main effects and their interactions. The major concern for this approach is the occurrence of non-constant variance for the number of cigarette puffs. Therefore, sensitivity analysis will be performed to evaluate the robustness of our assumptions. A generalized estimating equation (GEE) model uses sandwich estimators and thus is less affected by unequal variances, however, is more negatively impacted by the occurrence of missing observations. Additionally, a negative binomial regression approach will check if modeling the number of puffs as count variables provides a better fit to the data. The first mixed model will assume that participant characteristics are balanced between groups due to randomization and include only the three main effects and their interactions along with the stratification variables (gender, menthol status, and CPD [continuous, from the BL TLFB]) and the number of cigarette puffs from session 1 to increase precision.

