6.5. Exploratory Endpoint Analysis

The exploratory endpoints include the number of choices for cigarette puffs and e-cig puffs, number of choices to abstain from puffing, CES, Perceived Health risks, QSU, MNWS, PANAS, measures of cardiovascular function and biomarkers. We expect that biomarkers of exposure, and possibly other endpoints, will be skewed and will be log-transformed for analysis. These variables will be summarized using the geometric mean and differences between groups will be summarized by ratios of geometric means and 95% confidence intervals (CI). Any measurement that is obtained multiple times across lab sessions will be analyzed using a linear mixed model to

account for the within subject effect. Drop-out rates will be compared between the two cigarette groups with a chi-squared test.

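### SAP 6.3.1 adjusts cigarette puffs for Session 1 puffs taken on the randomised cigarette, and 6.4 and 6.5 state no matching covariates, so the VLNC–NNC effects on smoking, vaping and abstaining need not balance

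*Combined protocol and SAP*

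**What the plan says.** **Task.** The protocol (Overall Study Design) states that in each session "participants will be prompted via computerized instructions to make a series of 10 choices", and for Lab Sessions 2–5: "Each choice will be to either take 2 cigarette puffs, 2 e-cig puffs, or to abstain from puffing". SAP 5.1 likewise says that in Sessions 2–5 "each of the 10 choices is between taking 2 cigarette puffs, 2 e-cig puffs, or abstaining from both". In Session 1 only the assigned cigarette is offered, so the choice is cigarette or abstain.

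**Endpoints.** The primary endpoint is cigarette puffs, and "the result is an integer that ranges from 0 to 20" (SAP 6.3). E-cig puffs, also 0 to 20, are secondary (5.2). Counts of cigarette, e-cig and abstain choices, each 0 to 10, are exploratory (5.3). SAP 6.1 applies a 0.05 threshold to every endpoint.

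**Models for Sessions 2–5.**
- SAP 6.3.1, cigarette puffs: the first mixed model will "include only the three main effects and their interactions along with the stratification variables", plus Session 1 cigarette puffs. The stratification variables are gender, menthol status and CPD, with CPD entered as a continuous baseline TLFB value.
- SAP 6.4, e-cig puffs: the same factorial model with the stratification variables and unspecified baseline values. The same section says e-cig puffs are measured only from Session 2.
- SAP 6.5, choice counts: "Any measurement that is obtained multiple times across lab sessions will be analyzed using a linear mixed model". No covariates are named.

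**Timing.** The protocol (Lab Session 1 Procedures) places randomisation during Lab Session 1, and the only product smoked in that session's task is the assigned NNC or VLNC cigarette.

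**The concern.** The trial asks whether smoking given up under VLNC moves to vaping or to abstaining. SAP 2 names all three choices in the primary aim. Because the outcomes are a fixed split, a fall in one arm's cigarette choices must reappear, trial for trial, as e-cig choices or abstentions. The fitted arm effects will show this only if the three models share a covariate set.

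The covariate that matters is Session 1 cigarette puffs. SAP 6.3.1 itself compares the arms on Session 1 puffs as an outcome, then uses the same variable as a precision covariate for Sessions 2–5. If VLNC lowers Session 1 puffs, adjusting for them removes part of the VLNC effect from the primary result. If the e-cig and abstain models lack that covariate, the same change looks smaller for smoking than for its alternatives.

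The choice counts add a lesser problem. They repeat the puff endpoints on another scale, and a different covariate set could give the same data a second estimate and p-value.

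**Working it through.** **The plan's own figure.** SAP 3.2: 60 per group, effect size 0.60, two-sided 0.05. Noncentrality = 0.60 × √(60/2) = 3.29 on 118 degrees of freedom, giving power of 90.3%, against a stated minimum of 90%. It reproduces. It is for a plain two-sample comparison with no Session 1 covariate.

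**Identities.** Let C, E and A be the cigarette, e-cig and abstain choices in one of Sessions 2–5. Then C + E + A = 10, cigarette puffs = 2C and e-cig puffs = 2E, so

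cigarette puffs + e-cig puffs + 2A = 20.

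With one linear model, one covariate set and complete data, the arm effects therefore satisfy: cigarette + e-cig + 2 × abstain = 0. Under the same model, puffs and choices give identical p-values. In Session 1, A = 10 − puffs/2, so adjusting abstentions for their own Session 1 value amounts to adjusting for Session 1 puffs. Only e-cig puffs have no Session 1 value at all.

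**What adjustment removes.** Let τ be the arm effect with pre-randomisation covariates, δ the arm effect on Session 1 puffs with the same covariates, and b the slope of the outcome on Session 1 puffs in the adjusted model. Then

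τ(adjusted) = τ − b × δ.

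If only the cigarette model contains Session 1 puffs and the other covariates are common, the imbalance equals the amount removed, b × δ in absolute size. Illustration with assumed values: SD 4.9 puffs and effect size 0.60 give δ = 2.94 puffs in size. With b of 0.5 to 0.7, 1.5 to 2.1 puffs are removed.

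**Simulation.** The documents give no SD or effect size for this task, so the inputs are assumptions: 2,000 trials, 60 per arm, 10 multinomial choices in each of four sessions, person-level SD 1.0 on the logit scale, and the same personal cigarette propensity in Session 1 and Sessions 2–5. The VLNC log-odds effect on cigarette choice is −0.9 throughout. Arm effects come from least squares on person means, which equals the mixed-model estimate in balanced complete data.

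| Arm effect, in puffs | With Session 1 puffs | Without |
|---|---|---|
| Cigarette | 2 × (−0.512) = −1.02 | 2 × (−1.546) = −3.09 |
| E-cig | 2 × 0.265 = +0.53 | 2 × 0.780 = +1.56 |
| 2 × abstain | +0.49 (by balance) | 2 × 0.765 = +1.53 |
| Sum | 0 | 0.00 |

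- Session 1 puffs in the cigarette model only: −1.02 + 1.56 + 1.53 = +2.07 puffs.
- One common covariate set: the sum is zero to below 1e-13, with or without Session 1 puffs.
- A common set that includes Session 1 puffs restores balance but leaves all three effects shrunk.
- The cigarette arm effect is significant in 38% of trials with Session 1 puffs and in 98% without.
- Limiting case, an arm effect in Session 1 only: the adjusted coefficient averages 2 × 1.137 = +2.27 puffs and is significant in 93% of trials, although Sessions 2–5 have no arm effect.

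**Other assumed inputs.** The gap ranged from 1.3 to 2.4 puffs. One set gave cigarette effects of −0.4 to −1.0 puffs with Session 1 puffs, against −1.9 to −3.1 with pre-randomisation covariates, and a gap of 1.5 to 2.1. With Session 1 puffs dropped but covariates still unequal, the gap was about 0.12 to 0.15 puffs.

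**Puffs against choices.** If 6.5 is taken to mean no covariates, the two versions of the cigarette outcome disagree at 0.05 in 60% of trials in the tabulated scenario (27–71% across other inputs), and in 1–11% once Session 1 puffs are dropped.

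**Within-subject effects.** In complete data the e-cig nicotine contrast sums to zero (maximum 1e-16) whatever subject-level covariates are used. An arm-by-nicotine contrast does too (maximum 6e-16).

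**The case against.** Several points on the other side stand.

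- **Three distinct covariate sets.** A reader might infer these, but only 6.3.1 is fully written. Section 6.4 leaves its baseline values undefined and 6.5 is silent. The protocol (Statistical Approach) lists cigarette puffs, e-cig puffs and abstentions together as endpoints of interest and describes one primary model, so a common model is a possible reading.
- **Effects that cannot add up.** This is too strong. They add exactly under a common set in complete data, and otherwise need not. With no arm effect in any session, the imbalance is random around zero.
- **Inflated type I error from testing the primary outcome twice.** Not supported. The primary endpoint and model are fixed and the duplicate is labelled exploratory in both documents. Nothing lets it replace the primary result.
- **Exact duplication.** This assumes that both puffs of a chosen trial are taken. The protocol lists puff totals as task indices and notes that a puff may fail to activate the device.
- **Session 1 as baseline.** The protocol calls the no-e-cig session the baseline condition, which could justify adjusting for it. But it is a baseline for e-cig availability, not for cigarette type. The protocol's own first mixed model contains only the factorial terms.

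Also, no passage promises an additive account of adjusted effects, and descriptive means for complete sessions balance by themselves. That lessens the harm from imbalance, but not the shrinkage of the primary arm effect.

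**Conclusion.** The point holds for the VLNC–NNC main effect in Sessions 2–5. A post-randomisation covariate shrinks the primary arm effect, and because 6.4 and 6.5 do not state a matching set, the three arm effects need not balance. The gap is about 1.5 to 2 puffs on a 0–20 scale under assumed effects, and about 0.1 puffs without Session 1 puffs. Nearly all the size therefore comes from that covariate, and deleting the duplicate choice endpoints alone would gain little.

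The size depends on VLNC changing Session 1 puffs and on how strongly those puffs predict later ones; the documents give neither figure. The identities assume that all chosen puffs are taken. The finding does not extend to the e-cig nicotine and flavour effects or their interactions with arm when data are complete, nor to any type I error inflation from the exploratory duplicates.

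**What to change.** 1. In SAP 6.3.1, 6.4 and 6.5, analyse cigarette puffs, e-cig puffs and abstain choices from Sessions 2–5 with one identical mixed model and one set of pre-randomisation covariates: gender, menthol status and baseline TLFB CPD. Leave out Session 1 puffs. For these outcomes this also replaces the undefined baseline values in 6.4.
2. Report the three arm effects in one table, noting that cigarette + e-cig + 2 × abstain = 0 in complete data.
3. In SAP 5.3 and the protocol's Outcome Variables, label the cigarette and e-cig choice counts as rescaled puffs, not separately tested endpoints.

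**Cost.** Wording only, with two fewer tested endpoints. Some precision is lost: in the simulation the standard deviation of the cigarette arm estimate rose from 0.303 to 0.375 choices (0.375/0.303 = 1.24, or 24%), and with no arm effect from 0.312 to 0.412 (32%). These losses reflect the assumed strong link between Session 1 and later puffs. The same covariates must also enter all three models, even where one helps only a single outcome.
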